8.2.3. Electrocardiograms

For each participant, a single 12-lead ECG will be collected according to the SoA (Section 1.3). Electrocardiograms must be recorded before collecting any blood samples. Participants must be supine for approximately 5 to 10 minutes before ECG collection and remain supine but awake during ECG collection. Electrocardiograms may be obtained at additional times when deemed clinically necessary. All ECGs recorded should be stored at the investigational site.

Electrocardiograms will be interpreted by a qualified physician (the investigator or qualified designee).

If a clinically significant finding is identified the investigator will determine if the participant can be enrolled in the study.

8.2.4. Clinical Safety Laboratory Assessments

- See Section 10.2 Appendix 2 for the list of clinical laboratory tests to be performed and the SoA for the timing and frequency.
- The investigator must review the laboratory results and document this review. The laboratory results must be retained with source documents unless a Source Document Agreement or comparable document cites an electronic location that accommodates the expected retention duration. Clinically significant abnormal laboratory findings or other abnormal safety assessments are those that are not associated with the underlying disease, unless judged by the investigator to be more severe than expected for the participant's condition.
- All protocol-required laboratory assessments, as defined in Section 10.2 Appendix 2, must be conducted in accordance with the SoA, standard collection requirements, and laboratory manual.
- If laboratory values from non-protocol-specified laboratory assessments performed at an investigator-designated local laboratory require a change in participant management or are considered clinically significant by the investigator (e.g., serious adverse event [SAE] or AE or dose modification), then report the information as an AE.
- If a central vendor is used for the study, Lilly or its designee will provide the investigator with the results of laboratory tests analyzed by a central vendor, unless the safety laboratory test results may unblind the study.

8.2.5. Safety Monitoring

The Lilly clinical pharmacologist or CRP/CRS will monitor safety data throughout the course of the study.

8.2.5.1. Hepatic Safety

Not applicable.

8.2.5.2. Hypersensitivity Reactions

Many drugs, or their excipients particularly biologic agents, carry the risk of systemic hypersensitivity reactions. If such a reaction occurs, additional data describing each symptom should be provided to the sponsor in the eCRF.

Sites should have appropriately trained medical staff and appropriate medical equipment available when study participants are receiving study drug. It is recommended that participants who experience a systemic hypersensitivity reaction be treated per national and international guidelines.

In the case of generalized urticaria or anaphylaxis, additional blood and urine samples should be collected as described in Section 10.2 Appendix 2. Laboratory results are provided to the sponsor via the central laboratory.

8.2.5.3. Local Infusion Site Reactions

Symptoms or signs of local infusion site reactions may include erythema, induration, pain, pruritus, and edema.

Pre-specified local infusion site reaction assessments will be performed and collected at the time points indicated in the SoA (Section 1.3).

In addition, if a spontaneous ISR is reported by a participant or site staff at a non-prespecified time point, the local infusion site reaction eCRF will be used to capture additional information about this reaction (e.g., infusion site pain, erythema, induration, pruritis, and edema).

Local infusion site reactions, whether recorded as a result of the prespecified (or solicited) assessment or spontaneously reported reactions, will be recorded as AEs as clinically indicated.

Investigational site staff will be provided with separate instructions/training on how to evaluate local infusion site reactions and their severity in a consistent manner.

8.2.5.3.1. Exploratory Assessment using CCI Platform

8.2.6. Local Pain Measurements Using the Visual Analog Scale

Local pain measurements during bolus application will be assessed using the 100-mm validated VAS for pain. The VAS is a well-validated tool (Williamson and Hoggart 2005) to assess catheter insertion site pain. The VAS is presented as a 10-cm (100-mm) line, anchored by verbal descriptors, usually "no pain" and "worst imaginable pain." The participant is asked to mark the 100-mm line to indicate pain intensity. The participant will be asked to rate any pain associated during each inpatient infusion on a scale of 0 to 100 mm at times specified in the SoA (Section 1.3).

8.3. Adverse Events, Serious Adverse Events, and Product Complaints

Investigators are responsible for monitoring the safety of participants who have entered this study and for alerting Lilly or its designee to any event that seems unusual, even if this event may be considered an unanticipated benefit to the participant.

The investigator is responsible for the appropriate medical care of participants during the study.

The definitions of the following events can be found in Section 10.3 Appendix 3:

- AEs
- SAEs
- Product complaints

These events will be reported by the participant (or, when appropriate, by a caregiver, surrogate, or the participant's legally authorized representative).

The investigator and any qualified designees are responsible for detecting, documenting, and recording events that meet these definitions and remain responsible for following up on events that are serious, considered related to the study intervention or study procedures, or that caused the participant to discontinue the excipients infusion (see Section 7).

Care will be taken not to introduce bias when detecting events. Open-ended and non-leading verbal questioning of the participant is the preferred method to inquire about event occurrences.

After the initial report, the investigator is required to proactively follow each participant at subsequent visits/contacts. All SAEs will be followed until resolution, stabilization, the event is otherwise explained, or the participant is lost to follow-up (as defined in Section 7.3). For product complaints, the investigator is responsible for ensuring that follow-up includes any supplemental investigations as indicated to elucidate the nature and/or causality. Further information on follow-up procedures is provided in Section 10.3 Appendix 3.

8.3.1. Timing and Mechanism for Collecting Events

This table describes the timing, deadlines, and mechanism for collecting events.

Event	Collection Start	Collection Stop	Timing for Reporting to Sponsor or Designee	Mechanism for Reporting	Back-up Method of Reporting
Adverse Event					
AE	Signing of the informed consent form (ICF)	Follow-up visit	As soon as possible upon site awareness	AE eCRF	N/A

Event	Collection Start	Collection Stop	Timing for Reporting to Sponsor or Designee	Mechanism for Reporting	Back-up Method of Reporting
Serious Adverse Event					
SAE and SAE updates – prior to start of study intervention and deemed reasonably possibly related with study procedures	Signing of the informed consent form (ICF)	Start of intervention	Immediately, without undue delay	SAE paper form	SAE paper form
SAE and SAE updates – after start of study intervention	Start of intervention	Participation in study has ended	Immediately, without undue delay	SAE paper form	SAE paper form
SAE – after participant's study participation has ended and the investigator becomes aware	After participant's study participation has ended	N/A	Immediately, without undue delay	SAE paper form	N/A
Pregnancy					
Pregnancy in female participants	After the start of study intervention	10 hours after the last dose	Within 24 hours of learning of the pregnancy	SAE paper form	SAE paper form
Product Complaints					
Product complaint associated with an SAE or might have led to an SAE	Start of study intervention	End of study intervention	Within 24 hours of awareness	Product Complaint form	N/A
Product complaint not associated with an SAE	Start of study intervention	End of study intervention	Within 1 business day of awareness	Product Complaint form	N/A

Event	Collection Start	Collection Stop	Timing for Reporting to Sponsor or Designee	Mechanism for Reporting	Back-up Method of Reporting
Updated product complaint information	—	—	As soon as possible upon site awareness	Originally completed Product Complaint form with all changes signed and dated by the investigator	N/A
Product complaint (if investigator becomes aware)	Participation in study has ended	N/A	Promptly	Product Complaint form	

Abbreviations: AE = adverse event; N/A = not applicable; SAE = serious adverse event.

Serious adverse events, including death, caused by disease progression should not be reported unless the investigator deems them to be possibly related to study treatment.

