5.3. Lifestyle Considerations

Participants must adhere to lifestyle restrictions as outlined by the CRU throughout the duration of the stay in the CRU.

While in the CRU, participants will use their own insulin pump and glucose sensor and bring extra supplies including insulin, infusion set and reservoir, glucose sensor, batteries, blood glucose monitor and test strips, insulin syringe in case of pump failure, and fast-acting glucose tablets or gel to treat hypoglycemia. Participants should avoid hypoglycemia and prolonged hyperglycemia during the study procedures.

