10.3.1. Definition of AE

AE Definition

- An AE is any untoward medical occurrence in a participant administered a pharmaceutical product and which does not necessarily have a causal relationship with the study intervention. An AE can therefore be any unfavourable and unintended sign (including an abnormal laboratory finding), symptom, or disease (new or exacerbated) temporally associated with the use of a medicinal (investigational) product, whether or not related to the medicinal (investigational) product.

Events Meeting the AE Definition

- Any abnormal laboratory test results (hematology, clinical chemistry, or urinalysis) or other safety assessments (e.g., ECG, radiological scans, vital sign measurements), including those that worsen from baseline, considered clinically significant in the medical and scientific judgment of the investigator (i.e., not related to progression of underlying disease).
- Exacerbation of a chronic or intermittent pre-existing condition including either an increase in frequency and/or intensity of the condition.
- New conditions detected or diagnosed after study intervention administration even though they may have been present before the start of the study.
- Signs, symptoms, or the clinical sequelae of a suspected drug-drug interaction.
- Signs, symptoms, or the clinical sequelae of a suspected overdose of either study intervention or a concomitant medication. Overdose per se will not be reported as an AE/SAE unless it is an intentional overdose taken with possible suicidal/self-harming intent. Such overdose should be reported regardless of sequelae.

Events NOT Meeting the AE Definition

- Any clinically significant abnormal laboratory findings or other abnormal safety assessments that are associated with the underlying disease, unless judged by the investigator to be more severe than expected for the participant's condition.
- The disease/disorder being studied or expected progression, signs, or symptoms of the disease/disorder being studied, unless more severe than expected for the participant's condition.
- Medical or surgical procedure (e.g., endoscopy, appendectomy): the condition that leads to the procedure is the AE.
- Situations in which an untoward medical occurrence did not occur (social and/or convenience admission to a hospital).

- Anticipated day-to-day fluctuations of pre-existing disease(s) or condition(s) present or detected at the start of the study that do not worsen.

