10.3.2. Definition of SAE

If an event is not an AE per definition above, then it cannot be an SAE even if serious conditions are met (e.g., hospitalization for signs/symptoms of the disease under study, death due to progression of disease).

SAE is defined as any untoward medical occurrence that, at any dose:

a. Results in death

b. Is life-threatening

The term ‘life-threatening’ in the definition of ‘serious’ refers to an event in which the participant was at risk of death at the time of the event. It does not refer to an event, which hypothetically might have caused death, if it were more severe.

c. Requires inpatient hospitalization or prolongation of existing hospitalization

- In general, hospitalization signifies that the participant has been admitted to hospital for observation and/or treatment that would not have been appropriate in the physician’s office or outpatient setting. Complications that occur during hospitalization are AEs. If a complication prolongs hospitalization or fulfills any other serious criteria, the event is serious. When in doubt as to whether “hospitalization” occurred or was necessary, the AE should be considered serious.
- Hospitalization for elective treatment of a pre-existing condition that did not worsen from baseline is not considered an AE.

d. Results in persistent disability/incapacity

- The term disability means a substantial disruption of a person’s ability to conduct normal life functions.
- This definition is not intended to include experiences of relatively minor medical significance such as uncomplicated headache, nausea, vomiting, diarrhea, influenza, and accidental trauma (e.g., sprained ankle) which may interfere with or prevent everyday life functions but do not constitute a substantial disruption.

e. Is a congenital anomaly/birth defect

- Abnormal pregnancy outcomes (e.g., spontaneous abortion, fetal death, stillbirth, congenital anomalies, ectopic pregnancy) are considered SAEs.

f. Other situations:

- Medical or scientific judgment should be exercised in deciding whether SAE reporting is appropriate in other situations such as important medical events that may not be immediately life-threatening or result in death or hospitalization but may jeopardize the participant or may require medical or surgical intervention to prevent one of the other outcomes listed in the above definition. These events should usually be considered serious.

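### The exception to the disease-progression waiver on SAE reporting covers study treatment but not study procedures, unlike the rest of the plan

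*Protocol*

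**What the plan says.** The sentence under the event table in Protocol 8.3.1 reads: "Serious adverse events, including death, caused by disease progression should not be reported unless the investigator deems them to be possibly related to study treatment". Elsewhere the protocol uses the term study treatment for the excipient solution (Sections 4.1 and 6.1.1). The broader term, study intervention, is defined in Section 6 and includes medical devices.

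Other places count procedures as well:

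- Protocol 8.3: the investigator and designees "remain responsible for following up on events that are serious, considered related to the study intervention or study procedures".
- Protocol 8.3.1, first SAE row: before the start of intervention, a possible relation to study procedures is what triggers reporting.
- Protocol 9.3.5: AEs related to treatment or to protocol procedures are listed.
- SAP 9.3.4: treatment-emergent AEs are summarized by relationship to study drug and to protocol procedure, and serious AEs are listed.

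The definitions sit in Appendix 3. Section 10.3.2 says "If an event is not an AE per definition above, then it cannot be an SAE even if serious conditions are met" and gives as examples "hospitalization for signs/symptoms of the disease under study, death due to progression of disease". Section 10.3.1 removes signs and symptoms of the disease from the AE definition, but with a limit: "symptoms of the disease/disorder being studied, unless more severe than expected for the participant's condition". It also counts as an AE any "Exacerbation of a chronic or intermittent pre-existing condition including either an increase in frequency and/or intensity of the condition".

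Section 5.3 foresees glycemic trouble on the study day: "Participants should avoid hypoglycemia and prolonged hyperglycemia during the study procedures". The visible text does not say how serious hypoglycemia or ketoacidosis is to be classified for reporting, and it does not define disease progression.

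**The concern.** The disease under study is type 1 diabetes, and its acute serious events are the ones the protocol is wary of (Section 5.3; exclusion criteria 14 and 15). The study pumps deliver no insulin, so an investigator has little reason to link a hypoglycemic or ketoacidotic event to study treatment. A link to procedures is easier to entertain: participants run their own pump beside five study sets for most of a day, and have been told to keep their own set away from the central abdomen.

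The waiver contains a safeguard for doubtful causality, namely a possible relation to treatment. That safeguard leaves out the more plausible link in this trial. At stake is whether such an event reaches the sponsor immediately on the SAE form, and whether it appears in the SAP's listing of serious AEs.

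**Working it through.** The protocol gives no figure on this point. The check is a reading of the passages against each other, followed by a rough bound on size.

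**Four cases after the start of intervention**

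| Investigator's view of a serious glycemic event | Rule that applies | Reported as an SAE? |
|---|---|---|
| Caused by a study procedure | Not disease progression; the post-intervention SAE row of 8.3.1 has no causality filter | Yes, immediately |
| Sign of the disease, no worse than expected, not an exacerbation | Fails the AE definition in 10.3.1, so 10.3.2 excludes it | No |
| Meets the AE definition, attributed to the disease, possibly related to study treatment | Waiver in 8.3.1, exception met | Yes |
| Meets the AE definition, attributed to the disease, possibly related to study procedures only | Waiver in 8.3.1, exception not met on its wording | Open; the text permits withholding |

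The fourth row is the gap. The waiver sentence itself accepts that an SAE can be put down to the disease and still be possibly related to something in the study; otherwise its exception would be empty. For that overlap it protects treatment and omits procedures. The 10.3.1 qualifiers do not close the gap, because the waiver acts on events that are already SAEs and so have passed the AE definition. The same procedural doubt triggers reporting in the first SAE row, before infusion starts.

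The second row has a lesser problem. The hospitalization example in 10.3.2 is stated without the severity limit of 10.3.1. A site that reads 10.3.2 alone could treat every diabetes-related hospitalization as outside the AE definition.

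**Size**

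Inputs: 46 participants (Protocol 9.5); up to 36 days of participation, of which about 28 are screening (Synopsis). The documents give no rate of serious glycemic events, so 0.05 to 0.3 per participant-year is an assumption.

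- Exposure after screening: 46 × (36 − 28) / 365.25 = 1.01 participant-years.
- Expected serious glycemic events of any cause: 0.05 × 1.01 = 0.05 to 0.3 × 1.01 = 0.30.
- Chance of at least one: 1 − exp(−0.05 × 1.01) = 4.9% to 1 − exp(−0.3 × 1.01) = 26%.
- Part A infusion day only, to discharge at 12.5 h: 46 × 12.5 / (24 × 365.25) = 0.066 participant-years, giving a chance of about 0.3% to 2%.

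These are ceilings. The event at issue must also be attributed to the disease, be possibly related to a procedure, be judged unrelated to treatment, and be withheld. Each condition lowers the figure, and the documents give no basis for saying by how much.

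**The case against.** The strongest reply is that the waiver does not reach procedure-related events at all. It is confined to events caused by disease progression, and an acute episode provoked by a procedure is not progression of diabetes. On that view the unfiltered post-intervention row applies and the event is reported at once. This stands for any event clearly caused by a procedure. It does not settle the doubtful case, for which the exception was written.

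The AE rules are also protective. Severe hypoglycemia or ketoacidosis would usually count as an exacerbation, or as more severe than expected, and 10.3.2 applies only to events that fail the AE definition. That stands too. What counts as expected is left to judgment, however: exclusion criteria 14 and 15 admit a participant with one recent severe hypoglycemic episode, or with one emergency visit or hospitalization for poor glucose control.

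The event would probably not vanish. The AE row of 8.3.1 has no progression exception of its own, the SAP lists all AEs, Section 8 has sites raise immediate safety concerns with the sponsor at once, Section 8.3 asks for any unusual event to be flagged, and Section 8.2.5 has the sponsor monitor safety throughout. A reader who sees that there is no data monitoring committee might infer that nothing else would catch the event; these provisions show otherwise. They are still not the SAE route with its own timing and form.

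Finally, the suggested causal path is thin. The explicit instruction to keep the central abdomen free covers the days before arrival, when the first SAE row already names procedures (Section 4.1 adds a period that is redacted), and the documents describe no mechanism by which five insulin-free sets would upset glucose control.

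**Conclusion.** The mismatch is real and narrow. After infusion starts, the text permits a site to withhold an SAE that it attributes to diabetes but thinks possibly related to a study procedure, while the protocol's own follow-up and analysis sections and the SAP treat procedure-related events as in scope. This rests on two assumptions: that study treatment in 8.3.1 means the excipient solution, as it does elsewhere in the protocol, and that the investigator regards the event as disease progression in the first place.

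Two stronger readings are not supported. One is that severe hypoglycemia or ketoacidosis caused by procedures goes unreported if the protocol is followed; a clearly procedure-caused event is outside the waiver, and 10.3.1 keeps most severe events as AEs. The other is that the 5% to 26% chance measures missed reports; it covers any serious glycemic event of any cause, at assumed rates. The expected number of withheld events is well below that ceiling and very small. No VAS estimate, comparison or power statement changes. The point deserves correction because the consequence, though unlikely, is a serious event or death that does not reach the sponsor as an SAE.

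**What to change.** Reconcile 8.3.1 with Protocol 8.3, Protocol 9.3.5 and SAP 9.3.4 by extending the exception, so that an SAE attributed to disease progression is still reported when the investigator thinks it possibly related to study treatment or to study procedures. Reconcile the hospitalization example in 10.3.2 with 10.3.1 by attaching the same limit, that the exclusion does not apply when the event is more severe than expected for the participant.

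Nothing more is needed on this point. Deleting the waiver or the example, or ruling that every serious glycemic event must be an SAE, would go further than the inconsistency supports.

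The cost is two wording changes in the protocol. Existing forms, the sponsor's safety review and the SAP listings stay as they are. The downside is at most an occasional extra SAE report.

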8.4. Treatment of Overdose

There is a low risk of an overdose from either sodium citrate, magnesium chloride, Humalog diluent or treprostinil within this study.

The largest planned total dose of study treatment will be administered in Part A of the study when each participant will have 5 pumps and will receive a total dose of 270 U/day. The total amount of study treatment (sodium citrate, magnesium chloride, Humalog diluent or treprostinil) provided would be comparable to Humalog or Lyumjev administration to individuals with diabetes who are highly-insulin resistant and require more than 200 U of insulin per day.

Likewise, Reznik (2010) reviewed the data from 4 patients with type 2 diabetes with insulin resistance who were placed on CSII therapy with a concentrated insulin to address their daily insulin requirements (192U-630U). Although rare, patients with extreme insulin resistance requiring 10,000 U of insulin per day have been reported (Lalej-Bennis et al. 1997).

Additionally, the total dose for each study treatment is well below any therapeutic level:

- Sodium citrate as it is listed in the FDA Generally Recognized as Safe (FDA 2015a) food additives database and total amount given (11.9 mg as trisodium citrate dihydrate) is within the limits identified for approved drug products in the FDA Inactive Ingredients in Approved Drugs database (FDA 2015b).
- Magnesium chloride is a cation primarily intracellular. The total planned dose in Part A is 13.5 μ mol magnesium (or 2.74 mg magnesium chloride hexahydrate) and is below the therapeutic use (Lavoisier magnesium chloride 2004):

Therapeutic Indication	Administration
Curative treatment of torsades de pointe (TdP)	Intravenous bolus in 8 mmol of magnesium cation
Treatment of acute hypokalemia associated with hypomagnesemia	Intravenous infusion from 24 to 32 mmol of magnesium cation daily
Magnesium supplement during electrolyte rebalance and parenteral nutrition	Intravenous infusion from 6 to 8 mmol of magnesium cation over 24 hours
Preventive and curative treatment of eclampsia crisis	Intravenous infusion of 16 mmol of magnesium cation, i.e. 3.5 g of magnesium chloride for 20 to 30 minutes.

Based on the drug label (Lavoisier magnesium chloride 2004), the first signs of overdose of hypermagnesemia include inhibition of knee jerks, feeling of heat, drowsiness, spoken speech disorders, muscular paralysis with respiratory disorders and at the most, respiratory and cardiac arrest.

- Treprostinil is approved in many European Member States for use in the treatment of pulmonary arterial hypertension (PAH) and is known as Remodulin® for SC administration (Remodulin SPC 2016). In Part A, participants will be administered a planned total dose of treprostinil of 2700 ng. The maximum total daily dose of treprostinil in the study will be a small fraction of the average Remodulin® therapeutic dose (53- to 1707-fold less; [Table 7](#)). Based on the drug label, the signs and symptoms of overdose with Remodulin® during clinical trials are extensions of its dose-limiting pharmacologic effects and include flushing, headache, hypotension, nausea, vomiting, and diarrhea. Most events were self-limiting and resolved with reduction or withholding of Remodulin®.

Table 7 Maximum Estimated Treprostinil Dose in Diabetes Relative to Treprostinil Doses for Pulmonary Arterial Hypertension

Treprostinil Therapeutic Indication	Treprostinil Dose		Treprostinil dose in PAH patients vs Treprostinil Dose in study ^b
	ng/kg/min	ng/kg/day	
Total Dose in Part A			
• Maximum dose ^a	-	33.75	-
PAH (Remodulin®)^c			
• Lowest starting dose	1.25	1800	53-fold
• Average dose	9.3	13392	397-fold
• High dose	40	57600	1707-fold

Abbreviations: PAH = pulmonary arterial hypertension.

a Total Treprostinil dose in Part A (2700ng/80kg) assuming 80 kg body weight for an adult with T1DM

b Treprostinil dose in study vs PAH patients = treprostinil dose for PAH ÷ maximum treprostinil dose in study (Part A)

c Remodulin SPC 2016.

The sponsor does not recommend specific treatment for an overdose.

In the event of an overdose, the investigator/treating physician should:

1. Turn off all study pumps immediately.
2. Contact the medical monitor immediately.
3. Closely monitor the participant for any AE/SAE until study infusion no longer has a clinical effect or at least until the end of each visit. Refer to Section 10.3 Appendix 3 for reporting details.
4. Document the quantity of the excess dose, as well as the duration of the overdose, in the CRF.

